#### 12.4.4 Overall Best Response Assessment

Each patient will be classified according to his “best response” for the purposes of analysis of treatment effect. Best response is determined from the sequence of the overall response assessments as described in Table 5 in Section 12.8.1.

### 12.5 **Response Criteria for Neuroblastoma Patients with Bone Marrow Involvement**

#### 12.5.1 Bone Marrow Involvement

Bone marrow obtained within 28 days prior to study enrollment with tumor cells seen on routine morphology (not by immunohistochemical staining only) of bilateral aspirate or biopsy on one bone marrow sample.

Bone Marrow responses are determined by H&E Staining of bilateral bone marrow biopsies and aspirates.

Complete Response: No tumor cells detectable by routine morphology on 2 consecutive bilateral bone marrow aspirates and biopsies performed at least 21 days apart. Normalization of urinary catecholamines or other tumor markers if elevated at

THIS PROTOCOL IS FOR RESEARCH PURPOSES ONLY, SEE PAGE 1 FOR USAGE POLICY

study enrollment.

Progressive Disease: In patients who enroll with neuroblastoma in bone marrow by morphology have progressive disease if there is a doubling in the amount of tumor in the marrow AND a minimum of 25% tumor in bone marrow by morphology. (For example, a patient entering with 5% tumor in marrow by morphology must increase to  $\geq 25\%$  tumor to have progressive disease; a patient entering with 30% tumor must increase to  $> 60\%$ ).

In patients who enroll without evidence of neuroblastoma in bone marrow will be defined as progressive disease if tumor is detected in 2 consecutive bone marrow biopsies or aspirations done at least 21 days apart.

Stable Disease: Persistence of tumor in bone marrow that does not meet the criteria for either complete response or progressive disease.

#### 12.5.2 Overall Best Response Assessment

Each patient will be classified according to his “best response” for the purposes of analysis of treatment effect. Best response is determined from the sequence of the overall response assessments as described in [Section 12.7.1](#).

### 12.6 **Response Criteria for Patients with CNS Tumors**

#### 12.6.1 Measurable Disease

Any lesion that is at minimum 10 mm in one dimension on standard MRI or CT, for CNS tumors.

#### 12.6.2 Evaluable Disease

Evaluable disease is defined as at least one lesion, with no lesion that can be accurately measured in at least one dimension. Such lesions may be evaluable by nuclear medicine techniques, immunocytochemistry techniques, tumor markers, CSF cytology, or other reliable measures.

#### 12.6.3 Selection of Target and Non-Target Lesions

For most CNS tumors, only one lesion/mass is present and therefore is considered a “target” for measurement/follow up to assess for tumor progression/response. If multiple measurable lesions are present, up to 5 should be selected as “target” lesions. Target lesions should be selected on the basis of size and suitability for accurate repeated measurements. All other lesions will be followed as non-target lesions. The lower size limit of the target lesion(s) should be at least twice the thickness of the slices showing the tumor to decrease the partial volume effect (e.g., 8 mm lesion for a 4 mm slice).

Any change in size of non-target lesions should be noted, though does not need to be measured.

#### 12.6.4 Response Criteria for Target Lesions

THIS PROTOCOL IS FOR RESEARCH PURPOSES ONLY, SEE PAGE 1 FOR USAGE POLICY

Response criteria are assessed based on the product of the longest diameter and its longest perpendicular diameter. Development of new disease or progression in any established lesions is considered progressive disease, regardless of response in other lesions – e.g., when multiple lesions show opposite responses, the progressive disease takes precedence. Response Criteria for target lesions:

- **Complete Response (CR)**: Disappearance of all target lesions.
- **Partial response (PR)**:  $\geq 50\%$  decrease in the sum of the products of the two perpendicular diameters of all target lesions (up to 5), taking as reference the initial baseline measurements.
- **Minor Response (MR)**: A greater than or equal to 25% but less than 50% reduction in the product of the greatest tumor diameter and its perpendicular diameter on MRI scan, on a stable or decreasing dose of steroids with a stable or improving neurologic examination.
- **Stable Disease (SD)**: Neither sufficient decrease in the sum of the products of the two perpendicular diameters of all target lesions to qualify for PR, nor sufficient increase in a single target lesion to qualify for PD.
- **Progressive Disease (PD)**: 25% or more increase in the sum of the products of the perpendicular diameters of the target lesions, taking as reference the smallest sum of the products observed since the start of treatment, or the appearance of one or more new lesions.

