5.3.3 Part C: Surgical HGG Expansion Cohort

Patients with HGG requiring resection (Part C) will be treated at the recommended phase 2 dose (RP2D) determined from the phase 1 component (Part A) of this trial for 2 doses prior to undergoing scheduled resection of their tumors (*i.e.* Surgical resection should occur after dose on Day 8 but before dose on Day 15 of Cycle 1). After recovery from surgery with wound healed (minimum 3 weeks) and meeting criteria in [Section 5.2](#), patients can resume selinexor at the same dose and schedule and continue therapy to complete Cycle 1 and continue with Cycle 2. Patients who fail to recover from surgery within 6 weeks will be removed from protocol therapy.

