 Women of childbearing potential require a negative pregnancy test prior to starting treatment; sexually active patients must use two effective methods of birth control- including a medically accepted barrier method of contraceptive method (e.g., male or female condom). Abstinence is an acceptable method of birth control. Pregnancy testing is required prior to tumor imaging per institutional guidelines.

 If patients develop Grade 4 neutropenia then CBCs should be checked every 3 to 4 days until recovery to Grade 3

 Tumor Disease Evaluation should be obtained on the next consecutive cycle after initial documentation

THIS PROTOCOL IS FOR RESEARCH PURPOSES ONLY, SEE PAGE 1 FOR USAGE POLICY

- of either a PR or CR. Please note that for solid tumor patients, if the institutional investigator determines that the patient has progressed based on clinical or laboratory evidence, he/she may opt not to confirm this finding radiographically.
- 4 Patient diary (see [Appendix VII](#)) should be reviewed and uploaded into RAVE weekly during Cycle 1, and after completion of each treatment cycle.
  - 5 See [Section 8.3](#) for timing of PK studies.
  - 6 In consenting patients. See [Section 8.4](#) for timing of Pharmacodynamic studies.
  - 7 See [Section 8.5](#) for details of tissue studies.
  - 8 Part C: Observations are required as scheduled during protocol treatment only; *i.e.* weekly labs and observations are not required during the “surgery window” and may be held until resuming protocol therapy.
  - 9 Patients in Part C who interrupt treatment of Cycle 1 due to required resection should have scans repeated prior to resuming protocol therapy.
  - 10 Snellen eye chart should be used to assess visual acuity. If a decline in visual acuity occurs or other visual symptoms occur, the patient should be referred to an ophthalmologist for an examination.

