### 11.2.3 Evaluability for Response

Any patient who is enrolled who meets eligibility criteria for Part B and receives at least one dose of selinexor will be considered evaluable for response provided: (1) the patient demonstrates progressive disease or death while on protocol therapy; or (2) the patient is observed on protocol therapy for at least one cycle and the tumor is not removed surgically prior to the time complete response or partial response is confirmed, or (3) the patient demonstrates a complete or partial response as confirmed according to protocol criteria. Patients who demonstrate a complete or partial response confirmed by central review will be considered to have experienced a response for the application of the rule given in [Section 11.1](#). All other patients will be considered non-responders. All patients considered to have a response (CR, PR, or MR) must have imaging studies reviewed centrally at the COG. Centers will be notified by the COG about requests for scans of patients with stable disease. See [Section 8.2](#) regarding image submission instructions. The central review by COG will be provided as the final reviewed assessment of response when such becomes available.

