### 11.5 Pharmacokinetic and Correlative Studies and Response Analysis

A descriptive analysis of pharmacokinetic (PK) parameters of selinexor will be performed to define systemic exposure, drug clearance, and other pharmacokinetic parameters. The PK parameters will be summarized with simple summary statistics, including means, medians, ranges, and standard deviations (if numbers and distribution permit).

While the primary aim of this study is to evaluate the toxicity of selinexor, patients will have disease evaluations performed as indicated in [Section 8.1](#). Disease response will be assessed according to RECIST criteria for patients with solid tumors, or the criteria specified in [Section 12.6](#) for patients with CNS tumors, and will be reported descriptively.

Clinical benefit for Part B will be defined in one of two ways, either PR or CR on two consecutive 2D measurements on standard imaging (see [Section 12.6](#)) or as > 12 weeks from first dose without progressive disease, while clinical benefit in Part C will be defined as no visible disease progression six months from the start of treatment. Clinical benefit rate will be summarized separately for each of Parts B and C with 95% confidence intervals.

All these analyses will be descriptive and exploratory and hypotheses generating in nature.

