#### 12.6.7 Overall Response Assessment

The overall response assessment takes into account response in both target and non-target lesions, the appearance of new lesions and normalization of markers (where applicable), according to the criteria described in the table below. The overall response assessment is shown in the last column, and depends on the assessments of target, non-target, marker and new lesions in the preceding columns.

Target Lesions	Non-target Lesions	Markers	New Lesions	Overall Response
CR	CR	Normal	No	CR
CR	IR/SD	Normal	No	PR
CR	CR, IR/SD	Abnormal	No	PR
PR	CR, IR/SD	Any	No	PR
MR	CR, IR/SD	Any	No	MR
SD	CR, IR/SD	Any	No	SD
PD	Any	Any	Yes or No	PD
Any	PD	Any	Yes or No	PD
Any	Any	Any	Yes	PD

Each patient will be classified according to his “best response” for the purposes of analysis of treatment effect. Best response is determined as outlined in Section 12.7.1 from a sequence of overall response assessments.

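### The CNS response criteria keep the pre-operative scan as the Part C baseline, so the Cycle 1 resection could be recorded as a PR or CR in the descriptive response summaries

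*Combined protocol and SAP*

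**What the plan says.** - **Entry.** Section 4.1.4 requires measurable disease on imaging for Part C, so the initial baseline is a pre-operative scan.
- **Surgery.** Section 5.3.3 places the operation inside the treatment period: "Surgical resection should occur after dose on Day 8 but before dose on Day 15 of Cycle 1".
- **Rescan.** Footnote 9 to the Section 8.1 schedule, attached to the Cycle 1 tumor evaluation, says: "Patients in Part C who interrupt treatment of Cycle 1 due to required resection should have scans repeated prior to resuming protocol therapy". It does not call that scan a new baseline.
- **Response.** Section 12.6.4 measures PR as a fall of 50% or more in the summed products "of all target lesions (up to 5), taking as reference the initial baseline measurements". CR is "Disappearance of all target lesions". MR (25% to under 50%) has no reference scan named.
- **Progression.** PD is a 25% increase, "taking as reference the smallest sum of the products observed since the start of treatment", or a new lesion.
- **Use.** Section 12.6.7 classifies every CNS patient: "Best response is determined as outlined in Section 12.7.1 from a sequence of overall response assessments". Section 12.7.1 counts best response from the start of treatment, and Section 12.7.2 starts the duration clock when the size criterion is first met. Section 11.5 applies the Section 12.6 criteria "for patients with CNS tumors, and will be reported descriptively".
- **Evaluability.** Section 11.2.3 has a condition about surgical removal of the tumor, but it covers "Any patient who is enrolled who meets eligibility criteria for Part B and receives at least one dose of selinexor". Part B eligibility (Section 4.1.3.2) is limited to patients who do not need resection.

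**The concern.** The reference scan for PR is fixed before an operation that the cohort requires, and CR has no condition on why the lesion disappeared. A patient whose tumor is debulked can therefore meet the size criterion without any drug effect. Neither Section 12.6.7 nor Section 11.5 excepts Part C.

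At stake is the descriptive account of antitumor effect (aim 1.2.1). Section 11.1 describes sustained responses in recurrent non-DIPG high-grade glioma as very rare, so one or two surgical responses among a handful of patients would visibly change that account. The same patients would also be flagged for an extra scan (Section 8.1, footnote 3) and central review (Section 8.2.1), and would be given a duration of response.

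**Working it through.** **1. The plan's own response figures.** Section 11.1 gives the chance of at least one response among 10 Part B patients, 1 − (1 − p)^10.
- p = 0.20: 1 − 0.80^10 = 0.8926 (plan: 89.3%).
- p = 0.05: 1 − 0.95^10 = 0.4013 (plan: 40.1%).

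Both reproduce. Neither uses Part C patients, so nothing below changes them.

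**2. How much resection meets the PR size criterion.** If each diameter falls by a fraction d, the product falls by 1 − (1 − d)². Setting this to 0.50 gives d = 1 − √0.5 = 0.293. A 30% cut gives 1 − 0.70² = 51%.

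**3. Two illustrative patients (lesion sizes assumed).**

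| Scan | Product (mm²) | Against initial baseline | Against post-operative scan |
|---|---|---|---|
| A, entry 40 × 40 mm | 1600 | – | – |
| A, post-operative 25 × 25 mm | 625 | −60.9% | – |
| A, later on drug | 780 | −51.3% | +24.8% |
| B, entry 40 × 30 mm | 1200 | – | – |
| B, post-operative 15 × 10 mm | 150 | −87.5% | – |
| B, later 18 × 12 mm | 216 | −82.0% | +44.0% |

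- Patient A: 625/1600 = 0.391, a PR by size on the post-operative scan. Then 780/1600 = 0.4875, still a PR, and 780/625 = 1.248, just under the 25% PD threshold. Section 12.7.1, Table 3, turns PR followed by PR into a best response of PR, although the residual tumor has grown on drug. Against the post-operative scan this patient is SD.
- Patient B: also a PR by size after surgery, but 216/150 = 1.44 is PD against the smallest sum. Table 3 turns PR followed by progression into PD, so best response is not inflated here.

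The nadir rule thus removes some spurious responses. Those that remain are residuals that stay stable or grow by less than 25% up to the next assessment, and gross total resections with no visible recurrence by then.

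**4. How many patients.** Let q be the share of Part C patients whose resection meets the PR or CR size criterion; where Table 3 is applied, they must also not progress by the next assessment. The documents do not give q. With no drug effect, the expected number among 10 is 10q, and the chance of at least one is 1 − (1 − q)^10:

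| Assumed q | Expected of 10 | At least one |
|---|---|---|
| 10% | 1 | 65% |
| 25% | 2.5 | 94% |
| 50% | 5 | 99.9% |
| 100% | 10 | 100% |

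**5. Does Section 11.2.3 prevent this?** No. It is limited to patients meeting Part B eligibility, which excludes those requiring resection. Its three conditions are also alternatives, and the third admits any confirmed CR or PR.

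**6. Is the six-month measure affected?** No. PD is judged against the smallest sum since treatment began, so a smaller post-operative measurement becomes the reference for progression.

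**The case against.** The strongest defence is that objective response is not how Part C is judged. Aim 1.2.4 and Sections 11.1 and 11.5 assign radiographic response to the medical cohort and absence of progression at six months to the surgical cohort. The activity rule is confined to patients meeting Part B eligibility, and Section 11.5 calls its analyses descriptive and exploratory. All of this stands, and it limits the consequence.

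A second argument is that Part C patients, being outside Section 11.2.3, are simply not evaluable for response. This does not hold. Part A patients without high-grade glioma are outside it too, yet Section 11.5 still reports their response.

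A third is that the rescan before restarting drug is naturally a new starting point. That would be sensible, but the text does not say so. Section 12.6.4 names the initial baseline, and footnote 9 sits on the tumor evaluation entry of the schedule. Central review might catch the problem in practice, but no instruction tells the central reader to use the post-operative scan.

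A reader might also infer that a drug effect on residual tumor could not be separated from the surgery. The documents do not support that. The post-operative scan is required, so change from it can be calculated.

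**Conclusion.** The gap is real and should be closed, but its reach is narrow. Applied literally, a stated rule gives a wrong result for Part C: a resection that removes at least half the bidimensional product could be recorded as a PR, and a gross total resection as a CR, in the best-response and duration-of-response summaries. The number affected lies between none and 10 of up to 10 evaluable patients. It depends on the extent of resection, which the documents do not give, and on how many patients progress before the next assessment. The lesion sizes and values of q above are assumptions.

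Two stronger readings are tempting. One is that the protocol intends to credit surgery to selinexor; no section says so, and the result follows only from combining sections that omit a Part C exception. The other is that the Part C efficacy measure or a go/no-go decision is compromised; neither is, because PD uses the nadir and the activity rule excludes patients requiring resection.

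**What to change.** Add to Section 12.6.4 that, for Part C, the post-operative scan obtained before selinexor resumes (Section 8.1, footnote 9) is the baseline for CR, PR and MR, and that patients with no measurable residual disease on that scan are not evaluable for objective response and contribute only to the progression endpoint. The simpler alternative is to state that Part C is not evaluable for objective response at all. Choose one and cross-refer to it from Sections 11.5 and 12.6.7.

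Do not extend the surgical-removal condition of Section 11.2.3 to Part C. Every Part C tumor is operated on in Cycle 1, so that condition would conflict with using the post-operative scan as baseline. Because the conditions are alternatives, it would also leave the confirmed-response route open.

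The cost is wording only, since the scan is already required. Fewer Part C patients will be evaluable for response (none under the alternative), and any descriptive Part C response rate will look less favourable.

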## 4.1 Inclusion Criteria

- 4.1.1 Age: Patients must be  $\geq$  than 12 months and  $\leq$  21 years of age at the time of study enrollment.
- 4.1.2 BSA: Patients must have a BSA  $\geq$  0.84 m^2.
- 4.1.3 Diagnosis:
- 4.1.3.1 Part A: Patients with recurrent or refractory solid tumors, including lymphoma and CNS tumors, are eligible. Patients must have had histologic verification of malignancy at original diagnosis or relapse except in patients with intrinsic brain stem tumors, optic pathway gliomas, or patients with pineal tumors and elevations of CSF or serum tumor markers including alpha-fetoprotein or beta-HCG.
- 4.1.3.2 Part B: Patients with recurrent or refractory high grade glioma (WHO Grade III/IV) including disseminated tumors (excluding DIPG), not requiring surgical resection. Patients must have had histologic verification of malignancy at original diagnosis or relapse.
- 4.1.3.3 Part C: Patients with recurrent or refractory high grade glioma (WHO Grade III/IV) and requiring surgical resection (excluding DIPG and disseminated tumors), who in the opinion of treating physicians, are medically stable to receive 2 doses of selinexor (8-10 days of treatment) before undergoing surgery without compromising the success of the procedure. Note that if, in the opinion of treating physicians, current symptoms necessitate surgery before 2 doses will be able to be received, surgery should not be delayed to administer selinexor, and the patient would be ineligible for protocol therapy.
- 4.1.4 Disease Status:
- Part A: Patients must have either measurable or evaluable disease (see Sections [12.2](#) and [12.3](#) for definitions).
- Parts B & C: Patients must have measurable disease on imaging.
- 4.1.5 Therapeutic Options: Patient's current disease state must be one for which there is no known curative therapy or therapy proven to prolong survival with an acceptable quality of life.
- 4.1.6 Performance Level: Karnofsky  $\geq$  50% for patients  $>$  16 years of age and Lansky  $\geq$  50 for patients  $\leq$  16 years of age (See [Appendix I](#)). Note: Neurologic deficits in patients with CNS tumors must have been relatively stable for at least 7 days prior to study enrollment. Patients who are unable to walk because of paralysis, but who are up in a wheelchair, will be considered ambulatory for the purpose of assessing the performance score.
- 4.1.7 Prior Therapy

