Accrual to Parts B and C will only open once the MTD or recommended phase 2 dose has been determined in Part A, and may open concurrently with the PK expansion described above.

A maximum of 24 patients are expected to enroll in Parts B and C combined, assuming an inevaluability rate of 20%. We anticipate that each part of the study will require 6-12 months for enrollment.

Response for Part B will be defined as either MR, PR or CR on two consecutive 2D measurements on standard imaging done 4 weeks apart (See [Section 12.6](#)). Sustained responses are very rare in this cohort of recurrent non-DIPG HGGs. We will consider the agent of sufficient interest for further evaluation in this disease category if at least one PR or CR, or at least two MRs, is observed among 10 enrolled patients. A response rate of 20% or more would be evidence of sufficient activity. If the true response rate is 20%, then the probability of observing one or more responses among 10 evaluable patients is about 89.3%. If the response rate is 5%, then the probability of observing at least one response is about 40.1%.

Clinical benefit for Part C will be evaluated separately using the criteria of no visible disease progression six months from the start of treatment. If two or more of a cohort of up to six patients are unable to resume therapy within 6 weeks after surgery, the surgical arm will be declared not feasible. If Part B has fully accrued, Part C will close to further accrual.

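### Minor response in CNS tumors is scored on one lesion's product while PR, PD and the decrease side of SD use the sum over target lesions, so multi-lesion patients can be misclassified

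*Combined protocol and SAP*

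**What the plan says.** Section 12.6.4 classifies target lesions in CNS tumors by bidimensional products, but not on one scale.

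- PR is at least a 50% "decrease in the sum of the products of the two perpendicular diameters of all target lesions (up to 5"), against the initial baseline. PD is also defined on the sum, against the smallest sum since treatment began.
- MR is a 25% to under 50% "reduction in the product of the greatest tumor diameter and its perpendicular diameter on MRI scan", with steroid and neurologic conditions. It mentions neither a sum nor a reference scan.
- The decrease side of SD reads "Neither sufficient decrease in the sum of the products of the two perpendicular diameters of all target lesions to qualify for PR". This uses the sum and leaves out MR. The increase side reads "nor sufficient increase in a single target lesion to qualify for PD". This refers to one lesion, although PD uses the sum.
- The section's opening paragraph adds that "progression in any established lesions is considered progressive disease, regardless of response in other lesions".

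The overall-response table in Section 12.6.7 carries a target-lesion MR through to an overall MR and gives SD its own row.

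Section 11.1 counts MR, PR or CR on two consecutive measurements as a Part B response. It calls the agent of sufficient interest after one PR or CR, "or at least two MRs, is observed among 10 enrolled patients". Section 11.2.3 treats centrally confirmed CR or PR as a response for that rule and everyone else as a non-responder. Part B is open to "high grade glioma (WHO Grade III/IV) including disseminated tumors (excluding DIPG), not requiring surgical resection" (Section 4.1.3.2).

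**The concern.** MR should be the band just below PR on the same measurement. Here the two are measured on different things, and for a patient with two or more target lesions they do not join. A shrinking dominant lesion can give an MR while total measured tumor hardly changes. A fall in the sum well inside the 25% to 50% range can be scored SD, because the one product that counts fell too little or too much.

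The SD wording is a second, smaller fault. An MR that is not a PR on the sum also satisfies SD as written, and this applies to single-lesion patients too.

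At stake is the two-MR limb of the Part B rule, where one patient is half the threshold. MR also starts the clock for duration of response in Section 12.7.2. The primary aims are not affected.

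**Working it through.** **1. The plan's own figures.** Section 11.1 gives the chance of one or more responses among 10 evaluable patients. 1 − 0.80^10 = 89.3% and 1 − 0.95^10 = 40.1%, so both reproduce. They treat any single response as a success and do not model the two-MR limb.

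**2. Classifying example patients.** The products are assumed, in cm². Three further assumptions: the same lesion is followed over time, the lesion with the greatest diameter also has the greatest product, and the steroid and neurologic conditions are met. For growth in a single lesion I use PD's 25%, since the opening paragraph gives no threshold of its own.

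| Baseline → follow-up | Largest lesion | Sum | As written | MR on the sum |
|---|---|---|---|---|
| 10, 8 → 7, 9.6 | 7/10: −30% | 16.6/18: −7.8% | MR | SD |
| 10, 8, 8, 8, 8 → 7, 8, 8, 8, 8 | 7/10: −30% | 39/42: −7.1% | MR | SD |
| 10, 5 → 4, 5 | 4/10: −60% | 9/15: −40% | SD | MR |
| 10, 8, 8 → 8, 4, 4 | 8/10: −20% | 16/26: −38.5% | SD | MR |
| 10 → 7 (one lesion) | −30% | −30% | MR (SD wording also met) | MR |

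In row 1 the second lesion grows 9.6/8 = +20%, below 25%. No lesion grows in the other rows, so none of the examples is PD. In row 3 the single product has fallen too far for MR's upper limit of 50%, while the sum has not fallen far enough for PR.

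**3. Dependence on the reading.** If the greatest lesion is instead picked afresh at each scan, row 1 compares 10 with 9.6 (−4%) and row 2 compares 10 with 8 (−20%), and neither is an MR. Row 3 compares 10 with 5 (−50%, still outside MR) and row 4 compares 10 with 8 (−20%), so both stay SD. The MRs in rows 1 and 2 depend on following the same lesion. The missed responses in rows 3 and 4 do not.

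**4. Sensitivity of the Part B rule.** With PR/CR rate p, scored MR rate m and n = 10:

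P(go) = 1 − [(1 − p − m)^10 + 10·m·(1 − p − m)^9]

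The rates are assumed, and the formula takes MRs as counting, as in Section 11.1.

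| Scored MR rate | 0% | 5% | 10% | 15% | 20% |
|---|---|---|---|---|---|
| P(go), p = 0 | 0% | 8.6% | 26.4% | 45.6% | 62.4% |
| P(go), p = 5% | 40.1% | 45.8% | 57.2% | 69.1% | 79.4% |

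For example, at p = 0 and m = 5%: 1 − (0.95^10 + 0.5 × 0.95^9) = 8.6%. A five-point shift in the scored MR rate moves P(go) by about 6 points (40.1% to 45.8%) to 19 points (26.4% to 45.6%). These figures show how sensitive the rule is. They do not estimate the shift this wording would cause, which depends on the share of multi-lesion patients and is zero if there are none.

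**The case against.** The case for leaving this alone has real content.

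- **Few patients may be affected.** Section 12.6.3 says most CNS tumors present as one lesion. Section 4.1.3.2 makes disseminated tumors eligible, but disseminated disease need not supply two measurable target lesions. This stands: a reader might infer that multi-lesion patients are expected in Part B, and the documents show only that they may enroll.
- **MR may not count at all.** If Section 11.2.3 governs, only centrally confirmed CR or PR enters the rule and the MR wording cannot alter the decision. The best-response tables in Section 12.7.1 have no MR category either. On the other side, Section 11.1 names MRs explicitly, and Section 11.2.3 itself lists MR among the responses sent for central review. The conflict is unresolved, and it makes the consequence conditional.
- **Other safeguards apply.** MR needs two consecutive measurements, the steroid and neurologic conditions and central review, and progression anywhere overrides it. These narrow the problem, but none says which lesions to measure, and a central reader still needs a definition to apply.
- **A sensible reader would give the better category.** The separate rows in Section 12.6.7 support this for the MR/SD overlap. They do not repair the difference between one product and the sum.
- **The stakes are exploratory.** Antitumor effect is a secondary aim, and Section 11.5 calls these analyses descriptive and hypothesis-generating. That limits the severity.

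A reader might also infer that the Part B decision turns on which lesion shrinks and not on tumor burden. That goes too far: PR uses the sum, CR requires every target lesion to disappear, and one PR or CR settles the rule.

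**Conclusion.** The inconsistency is real, and no other section cures it. As written, and following the same lesion, a patient whose sum falls 7.8% can be an MR while one whose sum falls 40% is SD. The single-product fault is confined to patients with two or more target lesions. For single-lesion patients only the overlap between MR and SD remains.

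The effect on Part B cannot be sized from the documents, because no multi-lesion share is given. The decision changes only if three things hold together: MRs count toward the rule, no PR or CR is seen, and a misclassified patient moves the MR count across two. This should be corrected before Part B results are read, so that the definition is not chosen afterwards in a 10-patient decision. It does not threaten the primary aims.

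**What to change.** 1. In Section 12.6.4, define MR as a decrease of at least 25% but under 50% in the summed bidimensional products of all target lesions, measured from the initial baseline as for PR. Keep the steroid and neurologic conditions.
2. Define SD as meeting none of CR, PR, MR or PD. A 25% to 49% fall in the sum that fails the steroid or neurologic conditions is then SD and not unclassified. This also removes SD's reference to growth in a single lesion, which does not match the sum-based PD definition.
3. Reconcile Sections 11.1 and 11.2.3 on whether MRs count toward the Part B rule, and carry the answer into the central review instructions.

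The cost is two definitions in Section 12.6.4, one sentence in Section 11.1 or 11.2.3, and matching text for central review. PR and PD already need the summed products, so no new scans, measurements or data fields are required.
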